#### 8.4.1. Secondary SALT Endpoints

The following secondary SALT responder endpoints will be assessed:

Part A

- Percentage of patients achieving LOM criteria (SALT > 20) for each *dose reduction* condition at Weeks 4, 8, 12, 16, 20, and 24 (Period 2 ONLY). Note that these timepoints in Period 2 are equivalent to Weeks 28, 32, 36, 40, 44, and 48, respectively.
- Percentage of patients achieving LOM criteria (SALT > 20) for each *drug discontinuation* condition at Weeks 4, 8, 12, 16, 20, and 24 (Period 2 ONLY). Note that these timepoints in Period 2 are equivalent to Weeks 28, 32, 36, 40, 44, and 48, respectively.
- Percentage of patients achieving an absolute SALT score  $\leq 20$  at Weeks 4, 8, 12, 16, 20, and 24 (Period 1 ONLY)
- Relative change in SALT scores from Baseline at Weeks 4, 8, 12, 16, 20, and 24 (Period 1 ONLY)

Part B:

- Percentage of patients achieving the ROR criteria (SALT  $\leq 20$ ) at Weeks 4, 8, 12, 16, and 20
- Relative change in SALT scores from Part B Baseline at Weeks 4, 8, 12, 16, 20, and 24

Concert Pharmaceuticals, Inc.  
Statistical Analysis Plan – CP543.2004

Secondary endpoints on percentage of patients achieving an absolute SALT score of  $\leq 20$  or SALT  $> 20$ , will be assessed according to Section 8.4.

The continuous secondary SALT endpoint of relative change in SALT score from baseline at Weeks 4, 8, 12, 16, 20, and 24 in Part A Period 1 will be assessed with an MMRM, according to Section 8.4. The baseline SALT score will be as follows for each endpoint per Part:

Relative reduction is based on relative change from baseline.

Relative change in SALT score is derived as percent change of the follow-up SALT score, where baseline SALT score is the denominator (i.e. absolute change divided by the baseline score, multiplied by 100).

In addition, summary statistics for the mean, mean change, and mean relative change in total SALT score from Part A Period 1 baseline will be reported for Part A Period 1, Part A Period 2, and Part B. The mean and mean change in total SALT score from Part A Period 2 baseline will be reported for Part A Period 2 and Part B. Mean relative change from Part A Period 2 baseline will not be calculated as baseline values may be zero by design and would result in undefined relative changes. The mean, mean change, and mean relative change in total SALT score from Part B baseline will be reported for Part B.

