Patients in Part A, Period 2 will stay on their assigned dose for a maximum of 24 weeks or until they meet the criteria for loss of regrowth maintenance (LOM), defined as an absolute SALT score >20. Any patient meeting the LOM criteria at any assessment timepoint during Part A, Period 2 will enter Part B of the study and return to their original CTP-543 treatment from Part A, Period 1 (8 mg BID or 12 mg BID). Patients not meeting the LOM criteria (e.g., their absolute SALT score remains \leq 20) at the end of 24 weeks will have the opportunity to continue receiving treatment in the Open-Label Extension study (CP543.5001) or they will complete treatment at Week 24 and return in 4 weeks for the Post-Treatment Safety Follow-up.

Assessment of treatment response using SALT for efficacy will occur at 4, 8, 12, 16, 20 and 24 weeks. The primary efficacy analysis will be conducted when all patients have completed Week 24 of Part A, Period 2. The study design is depicted below.

Part A: Treatment and Dose Modification Phase

Part B: Re-Treatment Phase

Part B: Re-

Figure 2: CP543.2004 Study Design

LOM: Loss of Maintenance

Part B (Re-Treatment Phase)

Any patient from Part A, Period 2 meeting the LOM criteria (SALT > 20) will enter into Part B of the study and return to their original 8 mg BID or 12 mg BID dose assigned in Part A, Period 1. Patients will stay on their assigned dose for 24 weeks regardless of whether they meet the criteria for Restoration of Regrowth (ROR) or not. ROR is defined as the patient's attainment of an absolute SALT score ≤20. Assessment of treatment response using SALT for efficacy will occur monthly during the 24-week period. Patients will have the opportunity to continue receiving treatment in the Open-Label Extension study (CP543.5001) or they will complete treatment at Week 24 and return in 4 weeks for the Post-Treatment Safety Follow-up.

Safety

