receiving the 12 mg BID) or placebo. Patients in Part A, Period 2 will stay on their assigned dose for a maximum of 24 weeks or until they meet the criteria for loss of regrowth maintenance (LOM), defined as an absolute SALT score  $>20$ . Any patient meeting the LOM criteria at any assessment timepoint during Part A, Period 2 will enter Part B of the study and return to their original CTP-543 treatment from Part A, Period 1 (8 mg BID or 12 mg BID). Patients not meeting the LOM criteria (e.g., their absolute SALT score  $\leq 20$ ) at the end of 24 weeks will have the opportunity to continue receiving treatment in the Open-Label Extension study (CP543.5001) or they will complete treatment at Week 24 and return in 4 weeks for the Post-Treatment Safety Follow-up. The study design is depicted in the Study Flow Chart of the Appendix (Section 15.1).

An interim analysis to support regulatory activities related to an upcoming CTP-543 New Drug Application (NDA) submission will be conducted. The focus of the interim analyses will be on safety data and will occur following completion of Part A, Period 1. Additionally, after Part A, Period 1 completion, a PK population analysis will be completed. The PK analysis will be conducted by an outside vendor. This analysis will be described in a separate analysis plan and a separate report will be generated.

The primary efficacy assessment will be conducted when all patients have completed Part A, Period 2. An analysis of safety data will also be conducted. This analysis will be included in the NDA submission as an abbreviated report. Site personnel and patients will remain blinded to individual patient study treatments.

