#### 8.1.2. Assessment Time Windows

The visit schedule for all study assessments is provided in Appendix 15.2, by Part. For scheduled visits, there will be no reassignment of the analysis visit based on date. Unscheduled visits and early termination visits will be reassigned based on the analysis windows in the below table and the schedule of events. Assessments in part B will be windowed counting from the part B treatment start date. Assessments may only be re-assigned to visits where they were to be collected per the schedule of events. The latest assessment in a window will be selected as the visit used in summaries, unless otherwise specified. All visits will be included in by-patient data listings.

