### **8.2.1. Computation of the Primary Endpoints**

The SALT is a measure of hair loss that quantifies the amount of scalp surface without hair in a pre-specified quadrant of the scalp (right side, top, left side, back), that is further summed after applying a quadrant-specific multiplier indicative of scalp surface area contribution, to provide an overall score of total hair loss. An example of the SALT assessment can be found in Appendix 18.2 of protocol.

The primary endpoints for each Part of the study consist of deriving and categorizing the individual overall SALT scores ( $\leq 20$  versus  $> 20$ ).

Due to the variable time on study for each patient within Part A Period 2, the primary analysis visit will be the End of Part A Period 2, where the last observed non-missing SALT value is selected for each patient. Otherwise, missing data will not be imputed for this descriptive, exploratory study.

Patterns of missing values across visits will be listed and summarized with numbers and percentages by treatment and visit.

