## **8.4. Secondary Endpoints**

Analyses for secondary endpoints will be performed using the Efficacy Population.

Missing values will not be imputed.

Concert Pharmaceuticals, Inc.  
Statistical Analysis Plan – CP543.2004

For the secondary endpoints of proportions or percentages of patients achieving specified improvement criteria (hereinafter, “secondary responder endpoints”), pairwise treatment group differences in percentages and 95% CIs will be calculated in Part A Period 1 only.

Observed counts and percentages of responders will be summarized by treatment group for each Part/Period. 95% confidence intervals for percentages of responders and/or non-responders will be calculated using the binomial approximation with a Wald continuity correction.

For the secondary endpoints of absolute or relative changes (hereinafter, “continuous secondary endpoints”), continuous secondary endpoints will be summarized with descriptive statistics only and no treatment differences will be calculated. Descriptive statistics will include the number of subjects with data, mean, standard deviation, median, minimum, and maximum.

For Part A Period 1 only, treatment differences for continuous secondary endpoints will be assessed with a mixed-effect model of repeated measures (MMRM). Baseline SALT score will be included as a model covariate. Treatment group comparisons at each visit will be based on least squares (LS) mean estimates. An unstructured covariance matrix will be used to model the within-subject errors. Should the model fail to converge, an alternative autoregressive covariance matrix will be used instead. The Kenward-Roger approximation will be used to estimate the denominator degrees of freedom. Assuming that the data are MAR, the estimates of the treatment differences calculated from the MMRM described above are unbiased. Standard descriptive statistics will be reported for each time point on the values and changes from baseline along with the LS means, standard errors, 95% CIs and differences between treatment groups reported with LS means, standard errors, and 95% CIs. P-values will not be displayed.

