Table	14.1.8.1	Summary of Prior Medications	Safety Population	
Table	14.1.8.2.1	Summary of Concomitant Medications — Part A Period 1	Safety Population	Y
Table	14.1.8.2.2	Summary of Concomitant Medications — Part A Period 2	Safety Population	Y
Table	14.1.8.2.3	Summary of Concomitant Medications — Part B	Safety Population	
Table	14.2.1.1	Part A Period 2 Co-Primary Endpoints: Patients with Loss of Regrowth Maintenance (SALT Score $>20$ ) versus Responders (SALT Score $\leq 20$ )	Efficacy Population	Y
Table	14.2.1.2	Part B Primary Endpoint: Patients with Restoration of Regrowth (SALT Score $\leq 20$ ) at Week 24	Efficacy Population	
Table	14.2.2.1	Patients with Absolute SALT Score $\leq 20$ at Weeks 4, 8, 12, 16, 20, and 24 — Part A Period 1	Efficacy Population	Y
Table	14.2.2.2	Patients with Loss of Regrowth Maintenance (SALT Score $>20$ ) or Response (SALT Score $\leq 20$ ) at Weeks 4, 8, 12, 16, 20, and 24 — Part A Period 2	Efficacy Population	Y
Table	14.2.2.3	Patient with Restoration of Regrowth (SALT Score $\leq 20$ ) at Weeks 4, 8, 12, 16, 20, and 24 — Part B	Efficacy Population	

Concert Pharmaceuticals, Inc.  
Statistical Analysis Plan – CP543.2004

Type	Number	Title	Population	For abbreviated report?
Table	14.2.2.4	Mixed Model for Repeated Measures Analysis of Relative Change from Part A Period 1 Baseline in Total SALT Scores by Treatment Group and Visit — Part A Period 1	Efficacy Population	Y
Table	14.2.2.6.1	Mean, Mean Change, and Mean Relative Change from Part A Period 1 Baseline in Total SALT Scores by Visit — Part A Period 1	Efficacy Population	Y
Table	14.2.2.6.2	Mean, Mean Change, and Mean Relative Change from Part A Period 1 Baseline in Total SALT Scores by Visit — Part A Period 2	Efficacy Population	Y
Table	14.2.2.6.3	Mean and Mean Change from Part A Period 2 Baseline in Total SALT Scores by Visit — Part A Period 2	Efficacy Population	Y
Table	14.2.2.6.4	Mean, Mean Change, and Mean Relative Change from Part A Period 1 Baseline in Total SALT Scores by Visit — Part B	Efficacy Population	
Table	14.2.2.6.5	Mean and Mean Change from Part A Period 2 Baseline in Total SALT Scores by Visit — Part B	Efficacy Population	
Table	14.2.2.6.6	Mean, Mean Change, and Mean Relative Change from Part B Baseline in Total SALT Scores by Visit — Part B	Efficacy Population	
Table	14.2.2.7.1	Summary of Missing SALT Scores by Treatment Group and Visit — Part A Period 1	Efficacy Population	Y

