Figure	14.2.2.1.4	Restoration of Regrowth (SALT Score $\leq 20$ ) by Treatment across Time — Part B	Efficacy Population	
Figure	14.2.2.2.1	SALT Scores by Treatment across Time — Part A Period 1	Efficacy Population	Y
Figure	14.2.2.2.2	SALT Scores by Treatment across Time — Part A Period 2	Efficacy Population	Y
Figure	14.2.2.2.3	SALT Scores by Treatment across Time — Part B	Efficacy Population	

Concert Pharmaceuticals, Inc.  
Statistical Analysis Plan – CP543.2004

Type	Number	Title	Population	For abbreviated report?
Figure	14.2.2.3.1	Mean Change from Part A Period 1 Baseline in Total SALT Scores by Treatment across Time — Part A Period 1	Efficacy Population	Y
Figure	14.2.2.3.2	Mean Change from Part A Period 1 Baseline in Total SALT Scores by Treatment across Time — Part A Period 2	Efficacy Population	Y
Figure	14.2.2.3.3	Mean Change from Part A Period 2 Baseline in Total SALT Scores by Treatment across Time — Part A Period 2	Efficacy Population	Y
Figure	14.2.2.3.4	Mean Change from Part A Period 1 Baseline in Total SALT Scores by Treatment across Time — Part B	Efficacy Population	
Figure	14.2.2.3.5	Mean Change from Part A Period 2 Baseline in Total SALT Scores by Treatment across Time — Part B	Efficacy Population	
Figure	14.2.2.3.6	Mean Change from Part B Baseline in Total SALT Scores by Treatment across Time — Part B	Efficacy Population	
Figure	14.2.2.4.1	Relative Change in Total SALT Scores by Treatment across Time — Part A Period 1	Efficacy Population	Y
Figure	14.2.2.4.2	Relative Change from Part B Baseline in Total SALT Scores by Treatment across Time — Part B	Efficacy Population	
Figure	14.2.4.1	Kaplan-Meier Plot for Time to First Loss of Regrowth Maintenance (SALT Score >20) — Part A Period 2	Efficacy Population	Y
Figure	14.3.4.1	Key Clinical Laboratory Values: Hematology Parameters — Part A Period 1	Safety Population	Y
Figure	14.3.4.2	Key Clinical Laboratory Values: Hematology Parameters — Part A Period 2	Safety Population	Y
Figure	14.3.4.3	Key Clinical Laboratory Values: Hematology Parameters — Part B	Safety Population	
Listing	16.1.1	Randomization Codes	All Randomized	Y
Listing	16.1.10.1	Clinical Laboratory Reference Range		Y
Listing	16.2.1.1	Patient Disposition	All Randomized	Y

Concert Pharmaceuticals, Inc.  
Statistical Analysis Plan – CP543.2004

Type	Number	Title	Population	For abbreviated report?
Listing	16.2.1.2	Screen Failures		Y
Listing	16.2.1.3.1	All Patient Visits — Part A	All Randomized	Y

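### The Period 2 by-visit SALT means leave out everyone who lost regrowth at an earlier visit, so they understate loss and can fall while loss of maintenance accumulates

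*SAP*

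**What the plan says.** SAP 8.4.1 plans continuous SALT summaries for the dose-modification phase: "The mean and mean change in total SALT score from Part A Period 2 baseline will be reported for Part A Period 2". It also plans summaries from the Period 1 baseline over the same visits. SAP 15.4 lists the second baseline's table as "Mean and Mean Change from Part A Period 2 Baseline in Total SALT Scores by Visit" (Table 14.2.2.6.3). Table 14.2.2.6.2 and the mean-change Figures 14.2.2.3.2 and 14.2.2.3.3 are its companions. All four are marked for the abbreviated NDA report.

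Five rules decide who is in each mean:

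- Exit (SAP 3): "Any patient meeting the LOM criteria at any assessment timepoint during Part A, Period 2 will enter Part B of the study". Protocol 8.1 agrees, LOM being the event it refers to: "Patients in Part A, Period 2 will stay on their assigned dose for a maximum of 24 weeks or until they meet the criteria".
- Part B values cannot fill later Period 2 visits (SAP 8.1.2): "Assessments in part B will be windowed counting from the part B treatment start date".
- Secondary endpoints (SAP 8.4): "Missing values will not be imputed".
- SAP 8.2.1 takes the last non-missing SALT for the primary analysis visit, because time in Period 2 varies by patient. It then closes the door on other uses: "Otherwise, missing data will not be imputed for this descriptive, exploratory study".
- The repeated-measures model in SAP 8.4 is confined to Period 1.

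**The concern.** LOM exit is triggered by the variable being averaged. A patient who crosses 20 raises the mean once, at the crossing visit, and is absent from every later one. The patients left are those who have kept their hair, so the later means describe survivors and not the arm as re-randomised.

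The SAP saw the problem of unequal follow-up for its primary visit and solved it there, but did not extend the solution to the continuous summaries. No caveat is planned on these tables or figures. They are the planned mean summaries of how much hair is lost, as opposed to whether a threshold is crossed. A reader of the abbreviated report could take a falling or flat mean as stabilisation in an arm where most patients had already lost maintenance.

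**Working it through.** **The plan's own figure.** About 50 Responders per dose group, randomised 1:1 (SAP 7.2): 50 × 1/2 = 25 per arm. This matches Protocol 13.1 and is the starting denominator of each mean. No power calculation or loss rate is given, so every loss rate below is an assumption.

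**A worked arm.** Assume 25 patients, all with Period 2 baseline SALT 8. Per 4 weeks, 8 patients worsen by 14 points, 7 by 5, and 10 are stable. A value counts up to and including the first one above 20.

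- Week 4: (8×22 + 7×13 + 10×8)/25 = 347/25 = 13.9. The 8 fast losers cross 20 and leave.
- Week 8: (7×18 + 10×8)/17 = 206/17 = 12.1.
- Week 12: (7×23 + 10×8)/17 = 241/17 = 14.2. The 7 slower losers leave.
- Weeks 16 to 24: (10×8)/10 = 8.0.
- Last Period 2 value, all 25: (8×22 + 7×23 + 10×8)/25 = 417/25 = 16.7, a change of 16.7 − 8 = +8.7.
- Whole arm at Week 24 had loss continued without exit: (8×92 + 7×38 + 10×8)/25 = 1082/25 = 43.3.

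| Week | n | Observed mean change | Last value carried forward | Cumulative LOM |
|---|---|---|---|---|
| 4 | 25 | +5.9 | +5.9 | 32% |
| 8 | 17 | +4.1 | +7.3 | 32% |
| 12 | 17 | +6.2 | +8.7 | 60% |
| 16 to 24 | 10 | 0 | +8.7 | 60% |

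The observed mean change ends at zero in an arm where 60% have lost maintenance.

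**Does the mean always fall?** Simulated arms, with baseline SALT uniform on 0 to 20 and measurement noise SD 2. Loss is in points per 4 weeks. The last column is the chance, in an arm of 25, that the Week 24 mean change lies more than 2 points below an earlier peak.

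| Assumed loss | Observed mean SALT | LOM, Week 4 to 24 | Chance of fall |
|---|---|---|---|
| 60% lose about 15 | 19.0 to 9.1 | 43% to 65% | 100% |
| 30% lose about 15 | 14.5 to 9.0 | 23% to 38% | 95% |
| 80% lose about 15 | 22.0 to 9.1 | 57% to 82% | 99% |
| 20% lose about 5 | 11.0 to 9.2 | 7% to 28% | 40% |
| All lose about 8 | 18.0, peak 21.5 at Week 12, then 16.8 | 38% to 98% | 37% |
| All lose about 3 | 13.0 to 18.3, no fall | 13% to 82% | 5% |

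In the last row the mean does not fall, yet 18.3 is still well below the whole-arm 28.0.

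**How large is the gap?** Entry SALT uniform on 0 to 20 and noise SD 1.5; mean change from Period 2 baseline at Week 24.

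| Rise per 4 weeks | Observed | Last Period 2 value | Whole arm, no exit |
|---|---|---|---|
| Mean 4, SD 4 | about 1 (peak 6.5 at Week 8) | about 9 | not tabulated |
| Same, negative slopes set to zero | about 5 | about 10 | not tabulated |
| Mean 4, SD 1.5 | about 13 | 12 | 24 |
| Mean 4, SD 1 | about 17 | about 12 | 24 |

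The spread of slopes decides the result. With wide spread the observed mean sits far below the last-value mean. With narrow spread it sits above it. In the two narrow-spread rows, both fall short of the whole-arm loss.

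**The case against.** The strongest reply is that these are supporting summaries. Neither Protocol 13.2.1 nor the endpoint list in SAP 8.4.1 names a continuous Period 2 endpoint, no Period 2 treatment difference or p-value is computed, and the study is descriptive. Attrition is also disclosed: SAP 8.4 prints the number with data, Table 14.2.2.7.2 counts missing SALT by visit, Table 14.2.4.1 and Figure 14.2.4.1 give time to LOM, and Listing 16.2.6.1.3 shows individual SALT over time. All of this stands, and it limits the weight of the point. It does not remove it: those outputs show that patients are absent, but they do not correct the means or say on the table that LOM is a reason for absence.

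The second reply concerns remedy. Carrying the exit score forward at every visit is no clear improvement as the main display. With mean rise 4 and SD 1 it gives about 12 where the observed mean gives about 17 and the whole arm 24. It can also err the other way: with no true change and noise SD 3, it shows +0.8 against +0.1 observed, because it freezes a noisy crossing. This stands, and the fix below respects it.

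A reader might infer more than the documents support:

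- That placebo and dose reduction will look alike at Week 24. No loss rates are given for either arm, and the calculations compare no two arms.
- That the means must fall. They can; in three of six scenarios the chance was 40% or less.
- That all absence is caused by the outcome. Other discontinuations and visits missed for COVID-19 also remove patients.
- That the patients averaged all have SALT at or below 20. Those first crossing at a visit are counted there.
- That the figure titled "SALT Scores by Treatment across Time — Part A Period 2" shares the fault. Its title does not say that it plots means, and its layout is not shown.

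**Conclusion.** The point holds for Tables 14.2.2.6.2 and 14.2.2.6.3 and Figures 14.2.2.3.2 and 14.2.2.3.3. From the second Period 2 visit on, each by-visit mean is restricted to patients without earlier LOM and is biased towards less loss. The direction follows from the exit rule and the absence of imputation. The size does not: at Week 24 the observed change ranges from about 8 points below the last-value change (1 against 9) to about 5 above it (17 against 12), depending on how much loss rates differ between patients. The whole-arm benchmark is hypothetical, since by design these patients resume their original dose. Exit on SALT rounded to an integer (SAP 4) changes nothing material.

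The co-primary analysis and the Kaplan-Meier analysis of time to LOM are not touched. This is a cheap and worthwhile repair to descriptive outputs, not a threat to the study's main result.

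**What to change.** In SAP 8.4.1, add to the two tables and two mean-change figures an End of Part A Period 2 row or point: mean and mean change at the last observed Period 2 SALT, derived as in SAP 8.2.1, on the same patients as the co-primary analysis. State that this is the continuous summary to be interpreted. It describes every patient in that set when the assigned Period 2 regimen ended, and it lines up with the LOM percentages.

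Keep the observed-case by-visit means. Beside each, print n and cumulative LOM, with a footnote that later visits exclude patients with earlier LOM. Carry-forward at each visit may be added as supportive only.

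The cost is a sentence or two of SAP text, one row reusing an existing derivation, and a footnote; no new data are needed. The downside is that the last value freezes the score at exit. It generally understates the loss that would have followed, and can slightly overstate loss when a single noisy reading crosses 20. The footnote should say so.

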#### **8.4.2. Secondary SPRO Endpoints**

The following secondary SPRO responder endpoints will be assessed:

- Percentage of responders (defined as “satisfied” or “very satisfied”) on the SPRO scale at Weeks 12, 16, 20, and 24 (Part A Period 1 ONLY)

The SPRO is a single item questionnaire answered by the patient, designed to measure how satisfied alopecia areata patients are with their hair at the time of the assessment. The SPRO responses are on a scale of 1-5, where 1 = very satisfied, 2 = satisfied, 3 = neither satisfied nor dissatisfied, 4 = dissatisfied, and 5 = very dissatisfied. An example of the SPRO assessment can be found in Appendix 18.4.1 of the protocol.

A responder is defined as patients with answers of “very satisfied” or “satisfied” at each post-treatment visit on the SPRO. No missing data will be imputed for this endpoint.

